11.2.4 Study outcomes

Primary outcome: new stroke event (ischaemic or haemorrhagic) over 12 months

Secondary outcomes are:

- a) Major adverse cardiovascular events (MACE), defined as a combination of recurrent AIS, myocardial infarction (MI) and all-cause mortality over 3 and 12 months
- b) Recurrent AIS over 3 months and 12 months
- c) Any ICH reported by investigators or after central adjudication of relevant brain imaging over 3 months and 12 months
- d) sICH, in which ICH is related to substantial neurological deterioration or death according to various definitions over 3 months and 12 months
- e) Death or disability by shift analysis of scores on the mRS at 3 months and 12 months
- f) Separately on death and disability at 3 months and 12 months
- g) Neurological deterioration ≥ 4 points decline in NIHSS score over 7 days after randomisation
- h) Length of hospital stay
- i) HRQoL by the EuroQoL at 3 months and 12 months

11.2.5 Data collection and follow-up

Day 365 (± 1 month)

These assessments are to be undertaken by an investigator who was not involved in the clinical management of the patient, and blind to the randomised treatment allocation. On 365 \pm 30 days, all surviving patients will be evaluated through a telephone interview or at a face-to-face consultation. Use of BP lowering agents (**see Appendix 1**), antiplatelet agents, and adherence will be recorded. In addition to the mRS, cardiovascular events (CV death, non-fatal stroke, non-fatal myocardial infarction, major bleeding), HRQoL (using the EQ-5D) will be assessed.

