6.10.5 Follow up Data

Day 1 (Form C)

The primary goal of assessments within the first 24 hours will be to ensure adherence to the allocated the protocol. BP and administered medication will be recorded. BP will be recorded supine in the non-paretic arm from the automated, electronic device used at the Clinical Centre. BP will be recorded every 15 minutes for the first hour, then hourly for the next 5 hours, and 6 hourly from 6 hours to 24 hours. When i.v. boluses are given, HR and BP should be re-checked and recorded 5 and 15 minutes later. The following information will be recorded.

- BP
- BP lowering medication
- GCS and NIHSS scores at 24 hours
- Follow up brain imaging (CT brain and/or MRI) should be undertaken at 24-48 hours post-MT
- If other imaging investigations are performed (i.e. transcranial Doppler), these should be documented in the CRFs
- Antithrombotic medications
- Follow up blood tests
- Standard stroke care assessment

Day 7 or discharge if earlier (Form D)

On Day 7 or on the day of hospital discharge/transfer or death if prior to Day 7, the contact details of the patient or caregiver should be confirmed to facilitate follow up assessments. The following information will be recorded:

- GCS and NIHSS score
- Dependency assessed with the mRS
- BP
- BP lowering medication (medications used during Days 2 to 7)
- Medications and key specific treatment received during hospitalization
- Other aspects of acute stroke management during hospitalization

- Prognosis prediction from clinicians
- Date of discharge or transfer from hospital
- Repeat brain CT or MRI
- Healthcare costs and details of blood pressure lowering treatment.

BP Monitoring Chart (Form E)

As usual nursing care during the study period, the BP assessments in 7 days will be used to check adherence to BP management protocol.

Day 90 Follow-up (Form F)

These assessments are to be undertaken by an investigator who was not involved in the clinical management of the patient, and blind to the randomised treatment allocation. On 90±7 days, all surviving patients will be evaluated through a telephone interview or at a face-to-face consultation.

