Detailed resource utilization data, hospital billing data, physical function and patient reported quality of life data were collected for patients from the time of randomisation through 90-day follow-up. These data were used to calculate direct healthcare costs and QALY during the initial 90-day period based on international and national guidelines.^{34, 35}

- BP
- Dependency assessed with the mRS³⁶
- HRQoL measured by the EQ-5D³⁷
- Patient living status (e.g. home, high care)
- Any complications or hospitalization since going home
- Any medication currently used
- Healthcare related cost.

Death

Patients who have died prior to any of the above scheduled assessments, cause of death documentation will be collected with date and time of death. Copies of post-mortem reports, hospital record entry or death certificate, should be kept with the Patient Contact Details log to assist in trial monitoring by the CCC. An SAE form is to be completed for all deaths during the study period, stating the primary and underlying cause of death.

Withdrawal of allocated management and protocol violations

A form will be provided to record the date and circumstances surrounding any deviation from the protocol or missed assessments.

Consent

Consent will be documented in the patient's progress notes and CRF and the type(s) of consent obtained will also be recorded on the database.

Serious Adverse Events (SAEs)

All SAEs will be recorded on the SAE form, and completed on the electronic CRF or faxed/mailed from a printed form to the CCC within the prescribed time. Additional information may be requested to provide supplementary information on the event and outcome.

Table 2 Schedule of evaluations

Evaluation	Baseline (Prior Randomisation)	Day			365 ^b
		1	7 ^a	90 ^b	
Eligibility	X				
Brain imaging (CT ± angiogram or MRI± angiogram or DSA)	X	X	X		
BP	X (BP x 2)	X** q 15 min 1h 6h	X q12h	X	
HR	X				
ECG	X				
Consent	X				
Medical history, prior medications	X				
Details of rt-PA (if performed) and MT	X				
Physical exam GCS/ NIHSS	X	X	X		
Functional assessment with mRS	X		X	X	
HRQoL assessment with EQ-5D				X	
Routine blood tests	X	X			
BP lowering treatment		X	X	X	
Antithrombotic and other medications		X	X	X	
Standard stroke care		X	X		
Hospitalized or not			X	X	
Contact details for Follow-up		X	X		
Hospital service cost			X	X	
SAEs	X ^c	X	X	X	X

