11.1.6 Data collection and follow up

Day 90 ($\pm 7d$)

The adherence of the anticoagulation therapy in each randomised group will be collected through 90-day follow-up.

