11.2.3 Study design

This substudy – **Duration of DAPT** - is a pilot study imbedded in the main ENCHANTED2 study. Consent will be obtained prior to MT procedure, but randomisation will be undertaken post-MT at the same time of the main study, according to separate eligibility criteria. Randomised allocation (1:1 ratio) of intervention will be done via the same randomisation system as the main study, according to minimized method stratified by site and randomisation of BP intervention. The patients will be either allocated to short duration (6 weeks) or standard duration (3 months) of DAPT within 48 hours after AIS onset, and to be maintained on antiplatelet monotherapy (aspirin or clopidogrel) thereafter.

Study population

All patients randomised in the main trial, who have a final diagnosis of LAA-related AIS will be considered for enrolment in this sub-study. *In comparison to all other randomised patients, patients included in this substudy are followed up for 12 months.*

Inclusion and exclusion criteria

To be eligible for inclusion for this substudy, patients who has been enrolled into the main study **ARE** to still satisfy all of the following criteria:

- Final diagnosis of LAA confirmed by imaging during MT procedure

- b) Provision of written informed consent (or via an appropriate proxy, according to local requirements)

Patients will **NOT** be eligible if there is one or more of the following:

- c) Definite contraindication to both aspirin and clopidogrel

Treatment allocation

Short duration of DAPT

The patients will receive oral (including nasogastric if required) DAPT (aspirin 100 mg and clopidogrel 75 mg per day) for **6 weeks** within 48 hours after stroke onset if no PH confirmed by imaging after MT. If the patient is intolerance with aspirin or clopidogrel, cilostazol / dipyridamole can be used as a substitute.

Standard duration of DAPT

The patients will receive oral (including nasogastric if required) DAPT (aspirin 100 mg and clopidogrel 75 mg per day) for **3 months** within 48 hours after stroke onset if no PH confirmed by imaging after MT. If the patient is intolerance with aspirin or clopidogrel, cilostazol / dipyridamole can be used as a substitute.

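### In the DAPT-duration substudy, the assessor who must be blind also records the antiplatelet data that can reveal the arm, in the same assessment as the outcomes

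*Protocol*

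**What the plan says.** **Arms.** Under Protocol 11.2.3, patients are "allocated to short duration (6 weeks) or standard duration (3 months) of DAPT" and afterwards both arms continue on a single antiplatelet agent.

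**Day 90.** Protocol 6.10.5 (Form F) requires an assessor "blind to the randomised treatment allocation. On 90±7 days, all surviving patients will be evaluated". The items on that form include mRS, EQ-5D, complications or admissions since going home, and "Any medication currently used". The schedule of evaluations also has a row, "Antithrombotic and other medications", marked at day 90.

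**Day 365.** Protocol 11.2.5 again requires an assessor "blind to the randomised treatment allocation". The same paragraph says that use of BP-lowering agents, "antiplatelet agents, and adherence will be recorded". It continues: "In addition to the mRS, cardiovascular events (CV death, non-fatal stroke, non-fatal myocardial infarction, major bleeding), HRQoL (using the EQ-5D) will be assessed".

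**Safeguards elsewhere.** Protocol 13.4 and 13.5 set up blinded central reading of scans and a committee that reviews outcomes blinded. SAP 3.2 removes patients without a blind 90-day assessment from the per-protocol set, and SAP Table 17 counts non-blinded assessments. SAP 3.9 lists adherence among the main purposes of the substudies.

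**The concern.** Treatment is open label, so the design relies on whoever scores the outcome not knowing the arm. In this substudy the arm is defined entirely by how long two drugs are taken together, and the person who must not know the arm is asked about those drugs. If the drug questions come first, or are mixed with the outcome questions, the assessor can infer the arm before scoring mRS, completing EQ-5D or asking about new events.

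Two things are at stake. One is the blind for the interview-scored outcomes: Protocol 11.2.4 lists mRS and quality of life at 3 and 12 months as secondary outcomes of this substudy. The other is the quality of the adherence data. DAPT adherence is itemised only at day 365, long after either course should have ended.

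**Working it through.** The question is mainly one of procedure, so the check asks what each recorded item tells the assessor at each visit.

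**1. Day 90, current drugs.** Inputs:
- course lengths of 6 weeks (6 × 7 = 42 days) and 3 months, taken as 90 days because Protocol 6.8 equates the two;
- start within 48 hours, taken as day 0 to 2 after randomisation (assumption; Protocol 11.2.3 counts from stroke onset, the synopsis from randomisation);
- visit window 90 ± 7, so days 83 to 97, which is 15 days.

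First day on a single agent = start day + course length:
- short arm: 0 + 42 to 2 + 42 = day 42 to 44;
- standard arm: 0 + 90 to 2 + 90 = day 90 to 92.

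At the visit, a short-arm patient who followed the plan has been on a single agent for 83 − 44 = 39 to 97 − 42 = 55 days. For a standard-arm patient:

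| Visit day | Standard arm takes | Do current drugs separate the arms? |
|---|---|---|
| 83-89 (7 of 15 days) | two agents | yes |
| 90-91 (2 of 15) | depends on start day | partly |
| 92-97 (6 of 15) | one agent | no |

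If 3 months means calendar months (89 to 92 days), the days of clear separation run from 6 of 15 (days 83-88) to 9 of 15 (days 83-91). These are shares of the window, not of patients. The documents do not say how visits will spread over it, and departures from the assigned course would blur the picture.

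**2. Day 365, current drugs.** Both arms should have been on a single agent for months. Current use does not separate them.

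**3. Day 365, adherence.** If this means how long the two agents were taken together, the answer is the arm, or close to it. It would also rest on recall: 365 − 42 = 323 days after a week-6 stop. If it means adherence to current drugs, it does not reveal the arm, but then it does not measure adherence to the randomised course either.

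**4. Separation of tasks.** Protocol 6.10, 6.10.5, 11.2.3 and 11.2.5 and SAP 3.9 contain no rule that outcomes are scored before the drug items, and none that other staff collect the drug items.

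**5. The plan's own sample size.** The substudy figure reproduces on the risk-difference scale, with 10% in both arms, a margin of 1.4 × 10% − 10% = 4 points, one-sided 0.025 and 90% power:

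n per arm = (1.960 + 1.282)² × 2 × 0.10 × 0.90 / 0.04² ≈ 1182.1, rounded up to 1183; total 2 × 1183 = 2366.

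This agrees with Protocol 11.2.6. The present point does not dispute it, and the fix does not change it.

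**The case against.** The best reply has four parts.

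- **The events are reviewed elsewhere.** New strokes go to blinded endpoint review and scans to blinded reading. A serious event also reaches the coordinating centre through SAE reporting (Protocol 7.2.2). This stands in part. The committees can judge only what is forwarded to them, and the assessor influences which events are elicited at interview. For mRS and EQ-5D no other specific safeguard is described.
- **The word adherence is loose.** It may refer to current drugs. This is fair, and it is why the day-365 limb is conditional.
- **Page order belongs in the procedure manual.** Protocol 6.10 places the CRFs and completion guide there, and the manual is not among the documents. Its absence here does not prove that the order is unprotected. Still, the protocol gives one blind person both tasks, and a sentence there would settle the matter.
- **The substudies are pilots.** SAP 3.9 analyses stroke, ICH, death and SAEs, not mRS or quality of life. This stands and limits the importance of the point.

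Three stronger readings are tempting but unsupported:

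- *The anticoagulation substudy has the same problem.* Protocol 11.1.6 says "The adherence of the anticoagulation therapy in each randomised group will be collected through 90-day follow-up" but names no collector. Those arms differ only in start day, so current use at day 90 does not separate them.
- *The non-inferiority conclusion would be distorted by a calculable amount.* The documents give neither size nor direction for any ascertainment bias. Under-recording in the short arm would favour non-inferiority, and over-recording would work against it. SAP 3.9 sets no margin and plans no non-inferiority test. A false-positive rate at 2366 patients is also out of reach, since the whole trial plans 2257, of whom those with large artery atherosclerosis are only a part.
- *The main trial's primary outcome loses its blind.* The day-90 mRS is the same measurement, but substudy allocation is stratified by BP arm, so learning the DAPT arm does not disclose the BP arm.

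**Conclusion.** The concern holds for the DAPT-duration substudy, at minor severity. The protocol requires a blind assessor and gives that person, in the same assessment as the outcomes, items that can disclose the arm. At day 90 current antiplatelet drugs largely reveal it in the first half of the window and less so afterwards. At day 365 only a history of DAPT duration would do so.

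The exposure is confined to interview-scored mRS and EQ-5D and to which events are elicited. No numerical bias can be given. The adherence weakness does not depend on any assessor being biased: without a dated record near the time, adherence to the randomised course would rest on recall at about 12 months.

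The conclusion assumes that patients broadly follow their assigned course, that 3 months means about 90 days, and that no manual outside these documents already separates the tasks.

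**What to change.** 1. On Form F and on the day-365 form, have mRS, EQ-5D and the event questions completed and locked in the data-capture system before the antithrombotic and adherence items open. Alternatively, let the existing site coordinator enter those items on a separate page that the blind assessor does not see.
2. Add one dated field at day 90 for when the second antiplatelet agent was stopped, with an entry for still taking it. It should sit behind the same lock. Adherence then does not rest on 12-month recall.
3. State in Protocol 11.2.5 which form carries the day-365 items and whether adherence means adherence to the randomised course. The named forms end with Form F, and the schedule of evaluations, as far as its layout can be read, marks only SAEs at day 365.

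The cost is the page order of two electronic forms, one date field and a short protocol clarification. It needs no extra visit or staff, and sample size and treatment are unchanged.

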11.2.6 Sample size

In this and the other substudy, the aim is to recruit as many patients to inform the sample size estimates for the main study. Our preliminary sample size calculation to provide a reliable assessment of the treatment effect is outline below.

Ma et al. reported the proportion of post-stenting events of recurrent AIS and ICH over 12 months was 5.8% among patients with symptomatic intracranial atherosclerotic stenosis in China.⁶⁹ Considering on a broader inclusion of hospital sites and severe study population, the event rates were set up as 10%. As recommended by the United States Food and Drug Administration (FDA), the clinical margin representing the largest acceptable inferiority of the test to control is set at 50% of the margin of the excess risk. In this study, a relative non-inferiority margin of 40% (i.e. risk ratio 1.4) was used to provide assurance that short duration of DAPT retains at least 60% of the effects of reducing stroke recurrence risk compared with standard duration. A sample size of 2366 provides 90% power (1-sided $\alpha = 0.025$) to reject a non-inferiority margin of 1.4 from an expected event rate of 10% in the standard duration arm and assuming no true difference between the two durations.

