10. STATISTICAL CONSIDERATIONS

10.1 Sample Size

The study is designed with 90% power to detect an odds ratio (OR) of 0.77 at 90 days between the randomised groups in AIS patients with successful post-MT reperfusion using an ordinal logistic regression. Assuming a distribution of mRS in control group is 10.0%, 16.9%, 19.1%, 16.9%, 15.6%, 6.2%, and 15.3% for scores of 0 to 6, respectively, corresponding to a 6.48% absolute decrease in the proportion of patients experiencing a bad outcome (mRS of 3-6), from 54% down to 47.52%, according to the results of the meta-analysis made by HERMES collaboration.³⁸ This also translates to a 12% relative risk reduction (relative risk of 0.88). The sample size is 2257 subjects to demonstrate this treatment effect with 90% power and 4.82% type-1 error which we used the Haybittle-Peto boundaries taking into account 2 interim analyse during the study period. The sample size allows for 5% lost to follow-up and 5% drop-in/drop-out.

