11.1.5 Sample size

In this and the other substudy, the aim is to recruit as many patients to inform the sample size estimates for the main study. Our preliminary sample size calculation to provide a reliable assessment of the treatment effect is outlined below.

The results of Pre-TIMING study in Sweden revealed 12% of primary outcomes (4% of recurrent ischemic stroke, 3% of sICH, and 4% of all-cause mortality) in AF-related AIS patients with OAC therapy at 90 days.⁶² Given more severe patients are being enrolled in ENCHANTED2, the event rate is expected to be around 20%. A sample size of 2418 subjects provides 90% power to detect a 5% absolute (25% relative) risk reduction on a composite outcomes at 90 days between the randomised groups in AIS patients with successful post-MT reperfusion.

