11.2.2 Background and rationale

The effectiveness of APT for the secondary prevention of AIS is well recognized,⁶³ but the efficacy and safety of DAPT in MT-LVO patients remains controversial.^{64, 65} Whilst European guidelines do not recommend long-term DAPT in AIS patients, AHA/ASA guidelines (2018) recommend 21-days of DAPT with aspirin and clopidogrel commenced within 24 hours of symptom onset with minor stroke (Class IIa; Level of Evidence B) based on the Clopidogrel in High-Risk Patients With Acute Nondisabling Cerebrovascular Events (CHANCE)⁴¹ and Platelet-Oriented Inhibition in New TIA and Minor Ischemic Stroke (POINT)⁶⁹ trials. In CHANCE, 5170 Chinese minor AIS/high-risk TIA patients were randomly assigned to either DAPT (clopidogrel at an initial dose of 300 mg, followed by 75 mg per day for 90 days, plus aspirin at a dose of 75 mg per day for the first 21 days) or placebo plus aspirin (75 mg per day for 90 days), to show DAPT was superior in reducing the risk of recurrent stroke at 90 days (HR 0.68,

95% CI 0.57-0.81; $P <0.001$), with no significant increase in ICH risk (HR 1.41, 95% CI 0.95-2.10; $P = 0.09$) compared to monotherapy. The multinational POINT trial showed a 28% reduction in stroke recurrence with DAPT compared to aspirin monotherapy, but major bleeding events were double.⁶⁶ A meta-analysis published in 2013 included 14 RCTs of DAPT versus aspirin among 9102 AIS/TIA patients, showed that DAPT significantly reduce the risk of recurrent stroke in 3 months (RR 0.69, 95% CI 0.6-0.8), without increasing the major bleeding events (RR 1.35, 95%CI 0.7-2.59).⁶⁵ However, a recent meta-analysis including POINT further explored the optimal duration of DAPT to show that short-term (one month) reduced the risk of recurrent AIS (RR 0.53; 95% CI 0.37-0.78) without a significant increased the risk of major bleeding (RR 1.82; 95% CI 0.91-3.62).⁶⁷

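### DAPT substudy (Protocol 11.2.6): 2366 gives 90% power for an absolute 4-point margin, but only about 78% for the stated risk ratio of 1.4; the 60% retention claim has no derivation

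*Protocol*

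**What the plan says.** Protocol 11.2.6 gives the margin only on the ratio scale: "a relative non-inferiority margin of 40% (i.e. risk ratio 1.4) was used to provide assurance that short duration of DAPT retains at least 60" per cent of the reduction in recurrence achieved by the standard duration. The power statement repeats that scale. It claims 90% power from 2366 patients, at one-sided alpha 0.025 and with equal true rates, "to reject a non-inferiority margin of 1.4 from an expected event rate of 10% in the standard duration arm".

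Just before this, the section cites a regulatory convention under which the margin "is set at 50% of the margin of the excess risk". That excess risk is not quantified. The 10% event rate is raised from a 5.8% registry figure, with reasons given (wider range of sites, more severe patients).

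The other substudy is more explicit. Protocol 11.1.5 gives both scales: "A sample size of 2418 subjects provides 90% power to detect a 5% absolute (25% relative) risk reduction".

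Three other places bear on this:

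- **Protocol 10.1:** "The sample size is 2257 subjects to demonstrate this treatment effect" for the main trial.
- **Protocol 11.2.3:** "All patients randomised in the main trial, who have a final diagnosis of LAA-related AIS will be considered for enrolment in this sub-study", so the substudy draws on a subset of the main trial.
- **Protocol 11.2.1 and SAP 3.9:** 11.2.1 words a non-inferiority aim with a matching null hypothesis. SAP 3.9 gives feasibility as the purpose and contains no margin and no non-inferiority test.

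**The concern.** A margin of RR 1.4 and a margin of 4 percentage points are the same only when the control rate is exactly 10%. They are also different hypotheses with different test statistics. Under a ratio margin the limit moves with the control rate, which is itself estimated. That adds variance and lowers power even if the true rate is 10%. If 2366 was computed for one margin and reported for the other, the stated power is wrong for the margin on the page.

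The retention sentence raises a second problem. Preserving 60% of an effect means something only once the effect, its comparator and its scale are named. The section names none of these, and the claim stands beside a 50% rule whose base is also missing.

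At stake is the planning figure rather than this trial's main result. The section offers the calculation as input to a later trial, and a trial of 2366 patients tested against RR 1.4 would be about 1,000 patients short of 90% power.

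**Working it through.** **Inputs.** From 11.2.6: 10% events in both arms, one-sided alpha 0.025, 90% power, margin RR 1.4, total 2366. From 11.2.3: 1:1 allocation, so 1183 per arm. No dropout allowance is stated for this substudy. Normal quantiles are 1.960 and 1.2816, and (1.960 + 1.2816)² = 10.507.

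**Step 1: reproduce the stated figure.** At a 10% rate, RR 1.4 corresponds to 14% versus 10%, or 4 points. Treat that as a fixed absolute margin:

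- n per arm = 10.507 × 2 × 0.1 × 0.9 / 0.04² = 1182.1, rounded up to 1183. The total is 2366, an exact match.
- Power = Φ(0.04/√(0.18/1183) − 1.960) = 90.0%.

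The other substudy's figure reproduces on the same scale: 2 × ⌈10.507 × (0.2×0.8 + 0.15×0.85)/0.05²⌉ = 2418.

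**Step 2: use the margin as stated, RR 1.4.** The log-RR variance is 2 × (0.9/0.1)/n = 18/n, and ln 1.4 = 0.3365.

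| Method for RR 1.4 | Power at 2366 | Total N for 90% |
|---|---|---|
| Log-RR (Wald): Φ(0.3365/√(18/1183) − 1.960) | 77.9% | 2 × ⌈10.507 × 18/0.3365²⌉ = 3342 |
| Farrington-Manning score | 77.6% | 3386 |
| Linear contrast p₁ − 1.4p₂, unrestricted variance | 76.0% | 3500 |

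Simulation with 400,000 replicates at 1183 per arm gives 90.0% for the risk difference, 77.5% for log-RR and 77.8% for the score test. Other ratio-type readings do not give 2366 either: an odds ratio of 1.4 needs about 4126, a hazard ratio of 1.4 about 3720, log-RR at one-sided 0.05 needs 2724, and log-RR at 80% power needs 2496.

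**Step 3: vary the event rate (same rate p in both arms, 1183 per arm).** Absolute margin: Φ(0.04/√(2p(1−p)/1183) − 1.960). Ratio margin: Φ(0.3365/√(2(1−p)/p/1183) − 1.960).

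| Rate | RR equal to 4 points | Power, 4 points | Power, RR 1.4 |
|---|---|---|---|
| 5.8% | 0.098/0.058 = 1.69 | 98.6% | 53% |
| 8% | 1.50 | 94.8% | 67% |
| 10% | 1.40 | 90.0% | 78% |
| 12% | 1.33 | 84.9% | 86% |

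**Step 4: compare with the main trial.** If all 2257 main-trial patients were eligible and followed, n = 1128.5 per arm. Power would be 88.6% for 4 points and 75.9% for RR 1.4. The actual pool is smaller, because only patients with large artery atherosclerosis qualify.

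**Step 5: check the 60%.** As no reference effect is given, ask what reference RR (DAPT versus comparator) would make it true. Retention is 1 − 0.4/(1/RR − 1) on an excess-risk scale and 1 − ln 1.4/ln(1/RR) on the log scale. Setting retention to 60% requires RR = 1/(1 + 0.4/0.4) = 0.50 or exp(−0.3365/0.4) = 0.43. The only effect sizes in the document are the DAPT-versus-aspirin results in 11.2.2, including "DAPT significantly reduce the risk of recurrent stroke in 3 months (RR 0.69, 95% CI 0.6-0.8") and "reduced the risk of recurrent AIS (RR 0.53; 95% CI 0.37-0.78").

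| Point estimate in 11.2.2 | Retained, excess-risk scale | Retained, log scale | Margin under a 50% rule, 1 + 0.5(1/RR − 1) |
|---|---|---|---|
| 0.68 (HR) | 15% | 13% | 1.24 |
| 0.69 | 11% | 9% | 1.22 |
| 0.72 (from a 28% reduction) | −3% | −2% | 1.19 |
| 0.53 | 55% | 47% | 1.44 |

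None gives 60%. Only 0.53 would allow a margin of 1.4 under the 50% rule.

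**The case against.** The strongest reply is that the arithmetic is correct and only the label is loose. The power sentence pairs 1.4 with a 10% rate, which gives 14% versus 10%, and sizing on that difference yields 2366. No document specifies a test on the ratio scale. This explains how the number arose, but it does not make the statement right: the section twice gives the margin as a ratio, and the shortfall is there even at a true rate of exactly 10%.

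Second, nothing in this trial turns on the figure. The substudy is a pilot, the calculation is called preliminary and the SAP plans no non-inferiority test. That stands, and it limits the weight of the point. The protocol synopsis and 11.2.6 also already say that the substudies are meant to inform later sample sizes, so part of the clarification is a matter of emphasis.

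Third, the event-rate comparison depends on the rate chosen. That also stands: the protocol gives reasons for replacing 5.8%, and at 12% the two powers are nearly equal.

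Fourth, the retention percentages rest on formulas the protocol does not define and on mixed estimates from other populations and comparisons. Section 11.2.2 itself limits their application here. The 95% interval for 0.53 (0.37 to 0.78) includes both 0.50 and 0.43. All of this is fair. The percentages therefore show only that the 60% does not follow from anything in the document, not that 1.4 is an unsuitable margin.

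**Conclusion.** The concern holds. As written, 11.2.6 claims 90% power for a margin at which 2366 patients give about 78%, a shortfall of about 12 points. For RR 1.4, 90% power needs about 3342 to 3386 patients, which is 976 to 1020 more. These figures assume 10% in both arms, one-sided alpha 0.025, 1:1 allocation and no loss to follow-up. Loss would lower power: assuming 5% to 10%, log-RR power falls to about 76% to 73%. The number 2366 is correct for an absolute margin of 4 points, so the fault is the mismatch between the declared margin and the scale of the calculation.

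The 60% retention claim is unsupported. Whether 1.4 is a reasonable margin cannot be judged from the documents.

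The consequence for this trial is small, but the paragraph should be corrected before its figures are used to plan a later one.

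**What to change.** In Protocol 11.2.6:

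1. State one scale. Either give the margin as an absolute 4 percentage points (90% power at 2366) and note that it equals RR 1.4 only at a 10% event rate, or keep RR 1.4 and restate the power at 2366 as about 78%.
2. Delete the 60% retention claim, or derive the margin from a named reference effect with its comparator and scale, and reconcile it with the 50% rule cited beside it.
3. Say that 2366 is a planning figure for a later trial, since it exceeds the 2257 of the whole main trial, and that this pilot will not test non-inferiority. Reword the aim in 11.2.1 to agree with SAP 3.9.

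This costs protocol wording only and adds no patients here. If RR 1.4 is kept, a later trial with 90% power would need about 3342 to 3386 patients instead of 2366, before any dropout allowance.
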